1.3.2 Randomization and Blinding

This is an open-label extension study and no randomization was planned.

1.3.3 Sample Size and Statistical Power Considerations

This is an open-label, long-term continuation study. Sample size will be determined by those eligible after successful completion of Study 1042-0603.

2. STATISTICAL METHODS

2.1 GENERAL CONSIDERATIONS

In general, continuous variables will be summarized by number of subjects, mean, standard deviation (SD), median, minimum, and maximum values. Categorical variables will be summarized by counts and percentage of subjects in each category. If data is sparse, no summary table will be presented. Summary tables will present data by treatment received during the this study, i.e. Ganaxolone. Source data for the summary tables and statistical analyses will be presented as subject data listings, which include data collected on the electronic case report forms (eCRFs) as well as any derived variables for all enrolled subjects.

Baseline seizure activity will be determined by 8 weeks of retrospective recording in subject daily seizure calendars in Study 1042-0603.

Baselines for safety assessments are defined as the last non-missing value of the assessment before the first dose of treatment in Study 1042-0603.

2.1.1 Reporting Precision

Summary statistics will be presented to the following degree of precision, unless otherwise specified:

Statistics	Degree of Precision
Mean, Geometric mean, Median, Quartiles, Confidence limit boundaries	One decimal place more than the raw data.
Standard deviation, Standard error	Two decimal places more than the raw data.
Minimum, Maximum	The same as the raw data.
p-value	Rounded to 4 decimal places and therefore presented as 0.xxxx; p-values smaller than 0.0001 as '<0.0001'; p-values greater than 0.9999 as

	‘>0.9999’.
Percentage	One decimal place. A percentage of 100% will be reported as 100%. Percentages of zero will be reported as 0.

For weight and height, one decimal place will be used for summary statistics. Fractional numeric values will be presented with a zero to the left of the decimal point (for example, 0.12 – 0.30).

2.2 DEFINITIONS OF ANALYSIS POPULATIONS (ANALYSIS SETS)

2.2.1 Safety Population

All subjects who signed informed consent and took one dose of study medication in this study. In protocol, it is termed ITT Safety population.

2.2.2 Full Analysis Population (FAP)

Subjects who returned at least 25 days of seizure calendar data.

2.3 TIME WINDOWS FOR ANALYSIS

No visit window will be constructed for the analysis. Summary table will present data of scheduled visits. Data of unscheduled visits will only be reported in listings.

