8.3.4.2 Early Termination Procedures

Any subject who informs the site of an intention to withdraw from the study, or any subjects who are discontinued prior to the end of the study, will be asked to complete the procedures for Visit 7 (Study Completion/Early Term) which include: concomitant AED review, vital signs, physical and neurological exams, laboratory assessments, ECG, pregnancy test, C-SSRS, collection of adverse events, CGI-I, PCGI-I and seizure calendar review. The study drug will then be continuously tapered over one to two weeks, if possible, based on the dose and duration of treatment. A post-taper safety follow-up visit would then be completed. Subjects who are discontinued from the clinical investigation should return to their physician's care and continue appropriate medical treatment. Any AEs that have not resolved as of discontinuation will be followed until resolution. An end-of-study letter will be provided, if requested. Any follow-up information that is available will be added to the case report form up until the time that the database is locked.

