8.5.1.3 Schedule of Study Procedures

8.5.1.3.1 Visit 1 (same as Study1042-0603 Visit 10/Open Label Month 12)

1042-0603 Visit 10/Last Visit procedures: physical and neurological examination, 12-lead ECG, vital signs, blood and urine samples for safety laboratory tests and urine pregnancy test for WCBP, trough concomitant AED levels, subject diaries, C-SSRS, CGI-I, PCGI-I , AEs reviewed, medication compliance checked and study medication returned;

Additional 1042-0604 procedures: informed consent reviewed and signed; inclusion/exclusion and demographics/medical history reviewed; and 1042-0604 seizure calendars and study medication dispensed. Any Adverse Event that occurred in study 1042-0603 which is not resolved at the time of enrollment into 1042-0604 or is deemed significant by the Principal Investigator is to be captured in the subject's 1042-0604 medical history. If the frequency, severity or duration of this event changes in any way then it is to be captured as an Adverse Event in 1042-0604.

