8.5.1.3.7 Visit 7/Early Term Visit (Week 104; start of dose de-escalation period)

Concomitant AEDs reviewed, physical and neurological exams, vital signs, local ECG, safety laboratory tests, urine pregnancy test, C-SSRS, review safety and record AEs, subject calendar review, CGI-I, PCGI-I, study medication return and compliance check and dispense study medication.; dose de-escalation instructions given.

8.5.1.3.8 Visit 8 Safety Follow-up (Week 106; follow-up for end of dose de-escalation period)

Concomitant AEDs reviewed, brief physical and neurological exams, vital signs, safety laboratory tests, urine pregnancy test, C-SSRS, review safety and record AEs, subject calendar review and study medication return and compliance check.

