1.3 SUMMARY OF THE STUDY DESIGN

1.3.1 General Study Design and Plan

Study 1042-0604 is an open-label extension of Study 1042-0603, providing a two-year adjunctive ganaxolone treatment (900-1800 mg/d) to adult subjects with epilepsy consisting of partial-onset seizure (POS). Subjects who have completed all scheduled clinical study visits in the previous protocol 1042-0603 and have shown a minimum 35% improvement in mean seizure frequency per 28-days vs. baseline over the three 28-day periods preceding study entry, and acceptable tolerability, are eligible to participate.

Subjects will enter the study at their current dose of ganaxolone from study 1042-0603. The dose of ganaxolone may be adjusted for tolerability and response. Safety and tolerability will be assessed by diary record and at clinic visits approximately every four months. During the study if the patient fails to continue to meet the minimum improvement criteria (mean 28-day seizure frequency over the past three 28-day periods before the study visit showing 35% improvement over baseline) at any study visit the investigator should consider discontinuing the patient from the study. Efficacy will primarily be assessed based on daily seizure calendar entries.

Baseline for safety and efficacy evaluations will be each subject's baseline from Study 1042-0603.

The Schedule of Events is presented in [Table 1](#).

Table 1 Schedule of Events

WEEK	0	17	34	52	69	86	104 (Study completion/ET)	106 (Post-Taper Safety Follow-Up)	Unscheduled Visit ⁴
Visit Windows (Weeks)	±2	±2	±2	±2	±2	±2	±2	±2	
VISIT	V1 / Study 1042-0603 Visit 10	V2	V3	V4	V5	V6	V7	V8	
Informed consent	X								
Demographics & Medical HX ¹	X								
Inclusion/Exclusion criteria	X								
Concomitant AEDs ² Review	X	X	X	X	X	X	X	X	X
Safety Assessments									
Physical examination	X ³			X			X		
Physical brief exam		X	X		X	X		X	
Vital signs	X ³	X	X	X	X	X	X	X	X
Neurological examination	X ³			X			X		
Neurological brief exam		X	X		X	X		X	
ECG (12 lead) ⁵	X ³			X			X		
Safety Labs	X ³	X	X	X	X	X	X	X	X
Urine Pregnancy test (WCBP)	X ³	X	X	X	X	X	X	X	
Columbia Suicide Scale (C-SSRS)	X ³	X	X	X	X	X	X	X	
Review safety and record AEs	X ³	X	X	X	X	X	X	X	X
Efficacy Assessments									
Subject Calendar Review	X ³	X	X	X	X	X	X	X	
Clinician's Global Impression of Improvement	X ³	X	X	X	X	X	X		
Patient / Caregiver Global Impression of Improvement	X ³	X	X	X	X	X	X		
Study Medication									
Dispense study medication	X	X	X	X	X	X	X		

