7. SAFETY ANALYSIS

All safety analyses will be performed by treatment, i.e. Ganaxolone, in the Safety Population. Safety assessments include:

- AE
- Clinical laboratory tests
- Vital signs including temperature, blood pressure, pulse rate, and weight
- 12-lead ECG
- Physical and neurological examinations
- Columbia-Suicide Severity Rating Scale (C-SSRS)

Baseline is defined as the last non-missing value obtained before the first treatment in the preceding Study 1042-0603.

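### The Visit 7 row of the by-visit safety tables can pool early exits with Week 104 completers, and off-schedule liver tests enter no numeric laboratory summary (low severity)

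*SAP*

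**What the plan says.** SAP 2.3 sets the rule for all by-visit output: "No visit window will be constructed for the analysis. Summary table will present data of scheduled visits". It adds: "Data of unscheduled visits will only be reported in listings".

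The schedule of events (SAP 1.3.1, Table 1) gives completion and early termination (ET) one column, headed "104 (Study completion/ET"). Protocol 8.5.1.3.7 does the same under the title "Visit 7/Early Term Visit (Week 104; start of dose de-escalation period"). Under protocol 8.3.4.2, anyone who stops early "will be asked to complete the procedures for Visit 7 (Study Completion/Early Term"), whenever that happens.

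The affected summaries are laboratory (SAP 7.2), vital signs (7.3.1), physical examination (7.3.3) and C-SSRS (7.3.4). SAP 7.2 plans descriptive statistics by visit for chemistry, and listings of all laboratory data.

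Item 11 of protocol 8.3.4.1 sets liver thresholds. It requires a return visit with confirmatory testing within 72 hours of receiving the result, and then more frequent liver tests. Protocol 8.3.3 (exclusion 3) lets subjects enter before their Study 1042-0603 Visit 10 liver results are known, and assesses those results against item 11.

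SAP 9 records that the study ended early with low patient numbers.

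**The concern.** Safety and tolerability are the primary objective, and these tables are its main numeric output apart from adverse events.

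First, no SAP text says whether ET records appear under Visit 7, in a row of their own, or at the nearest scheduled visit. If they follow the schedule into Visit 7, a reader cannot tell what time in Study 1042-0604 that row represents. In a study that ended early, ET records could be much or all of the row.

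Second, the liver tests that item 11 calls for between scheduled visits fall under the unscheduled-visit rule. No table says how many subjects, out of how many, crossed the protocol's own liver thresholds, and by-visit statistics cannot supply that count when the qualifying value was off schedule.

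**Working it through.** The plan has no sample size, power or alpha figure to reproduce here. The inputs are the scheduled laboratory weeks (0, 17, 34, 52, 69, 86, 104, 106), the ±2-week windows, the 72-hour limit in item 11, and the protocol's statements on prior treatment and liver rates.

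**Span of each row**
- Visits 2 to 6: 2 + 2 = 4 weeks each.
- Visit 7: from just after Week 0 to 104 + 2 = Week 106, so up to 106 weeks.

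**What that span means.** It is time in Study 1042-0604, not total exposure. The protocol describes entry as "Visit 1 (same as Study1042-0603 Visit 10/Open Label Month 12"). The SAP places the safety baseline before that earlier study's treatment: "Baselines for safety assessments are defined as the last non-missing value of the assessment before the first dose of treatment in Study 1042-0603" (SAP 2.1; SAP 7 agrees: "Baseline is defined as the last non-missing value obtained before the first treatment in the preceding Study 1042-0603"). Taking 12 months as 52 weeks, open-label time in the Visit 7 row runs from about 52 + 0 = 52 to 52 + 106 = 158 weeks.

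**Illustration only.** Assume ET times are uniform over Weeks 0 to 104 (mean 52); the documents do not give their distribution. With ET share s, the mean actual week in the row is 104(1 − s) + 52s:

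| ET share | Mean actual week |
|---|---|
| 25% | 91 |
| 50% | 78 |
| 75% | 65 |
| 100% | 52 |

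**Spacing of scheduled liver draws**
- Gaps up to Visit 7: 17, 17, 18, 17, 17 and 18 weeks.
- Shortest gap with both windows used: 17 − 4 = 13 weeks = 91 days.
- Item 11 retest limit: 72 hours = 3 days after the result arrives. For a subject who stays in the study, the retest could fall on the next scheduled draw only if the result took at least 91 − 3 = 88 days to arrive.
- Visit 7 to Visit 8: nominally 2 weeks = 14 days, so 14 − 3 = 11 days.

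For continuing subjects before Visit 7, item 11 tests are therefore off schedule in practice. The SAP does not say how a repeat filed under a scheduled visit would be handled, although protocol 8.5.1.2 requires both original and repeat results in the CRF.

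**Expected number.** Protocol section 6 reports transient liver-test rises above 3×ULN in less than 1% of treated subjects. At the 350 maximum, the expected count is below 0.01 × 350 = 3.5. This is an expectation, not a cap. The rate does not transfer directly, because exclusion 3 screens out subjects with known ALT or AST above 3×ULN in Study 1042-0603, and actual enrolment was low.

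**Not affected.** ECG and neurological data are listed only. The adverse-event tables and the efficacy measures are not built by visit.

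**The case against.** The strongest reply is that few liver values escape the tables. Item 11 testing is confirmatory, so the first qualifying value is usually a scheduled, tabulated draw, and the by-visit statistics include the maximum. Item 11 sits among the withdrawal criteria. A subject who discontinues completes Visit 7 procedures, including laboratory tests, and then Visit 8. The recall test may itself be the ET Visit 7 draw, so the 88-day argument does not apply to that subject. All of this stands. It confines the gap mainly to subjects who continue under close monitoring.

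It is also fair that the protocol promised no threshold table, that complete listings can be read by eye when numbers are small, that liver findings recorded as adverse events are counted as TEAEs, and that the sparse-data rule in SAP 2.1 may turn some tables into listings. These reduce the gain. They do not supply a count with a denominator or a rule for ET records.

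A reader might infer three stronger things that the documents do not support:
- **That the Visit 7 row is mislabelled.** The SAP specifies no row title, and one naming both completion and ET would be accurate. CRF visit codes and table shells are not in the documents, and the database may already separate the two.
- **That off-schedule liver data are lost.** SAP 7.2 lists all laboratory data.
- **That the SAP dropped the laboratory flags and most-abnormal listings planned in protocol 8.7.1.4.** SAP 7.2 does not mention them and SAP 9 does not remove them. Silence does not show removal.

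**Conclusion.** The point holds as a low-severity improvement. Under SAP 2.3 the Visit 7 row can span up to 106 weeks of Study 1042-0604, against 4 planned weeks for each of Visits 2 to 6. Off-schedule liver values enter no numeric laboratory summary and no count against the protocol's own thresholds.

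The first part assumes that ET records carry the Visit 7 label, which the schedule suggests but the SAP never states as an analysis rule. The ET share is unknown; if nobody reached Week 104, the row is entirely ET. The second part rests on few subjects, perhaps none. No data are lost, and no reported result is shown to be wrong.

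**What to change.** **SAP 2.3.** Split Visit 7 by the disposition already summarised under SAP 3.1: 'Week 104 (completers)' for subjects recorded as completing, whatever their exact visit day, and 'Early termination' for all others. Show actual study day in Study 1042-0604 (median, range) for both rows. The study-day figures would also reveal subjects coded as completers when the study was stopped. Visit 8 can stay one post-taper row. The SAP 2.1 sparse-data rule still applies.

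**SAP 7.2.** Add one table of each subject's worst on-study ALT, AST and total bilirubin, using scheduled, ET, post-taper and unscheduled results. Give counts with a denominator, including zero, for the laboratory thresholds already in item 11:
- ALT or AST >3×, >5× and >8×ULN.
- ALT or AST >5×ULN for more than 2 weeks (11b), with a footnote on how duration is derived from collection dates.
- ALT or AST >3×ULN with total bilirubin >2×ULN (11c), with a footnote on whether the pair must share a collection date, which item 11 does not say.

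Show Visit 10 values separately, because they are held in the Study 1042-0603 database.

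**Cost.** SAP wording and modest programming on data already collected. The split rows are smaller, and the liver table may show few or no events. It is a reporting summary and changes no clinical rule.

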2.4 POOLING OF CENTERS

Data of all sites will be pooled together for analysis.

2.5 HANDLING OF MISSING DATA

Unless otherwise specified, missing data will not be imputed. All analyses will be based on available data.

2.6 ANALYSIS SOFTWARE

All summaries and statistical analyses will be generated using SAS® version 9.2 or later.

3. STUDY SUBJECTS

3.1 DISPOSITION OF SUBJECTS

Disposition will be summarized by treatment, i.e. Ganaxolone, in all enrolled subjects to this study.

The disposition will include the following:

- Subjects enrolled to Study 1042-0604
- Subjects in the Safety Population
- Subjects in the FAP
- Subjects completed study
- Subjects discontinued study
- Reasons for discontinuation

A listing of dispositions will be provided for all subjects.

3.2 PROTOCOL DEVIATIONS

The clinical team will identify deviations and the deviations will be recorded into the database.

A subject data listing will be provided.

4. DEMOGRAPHICS AND BASELINE CHARACTERISTICS

4.1 DEMOGRAPHICS AND BASELINE CHARACTERISTICS

Demographic data (age, gender, race, and ethnicity) and baseline characteristics (including height, weight and body mass index (BMI)) collected at study screening will be summarized using descriptive statistics by treatment, i.e. Ganaxolone, in the safety population and FAP, separately.

Height (in cm) = Height (in inches) * 2.54

Weight (in kg) = Weight (in lbs) * 0.4536

BMI (kg/m²) = Weight (kg)/[Height(m)²]

A subject data listing of demographics and baseline characteristics will be provided.

4.2 MEDICAL HISTORY

Medical history will be coded with the Medical Dictionary for Regulatory Activities (MedDRA) Terminology version 16.0. The number and percent of subjects with clinically significant medical history at screening will be summarized by system organ class (SOC) and preferred term (PT) by treatment, i.e. Ganaxolone, in safety population.

5. STUDY DRUG AND EXPOSURE

5.1 EXTENT OF EXPOSURE

Exposure to study medication will be summarized as a continuous variable, via the number of days of drug taken. Ganaxolone will be administered BID following the morning and evening meals. A missed dose of study medication may be taken later up to 8 hours before the next scheduled dose; otherwise, the missed dose should not be given. Treatment exposure and treatment compliance will be summarized using the Safety population.

- Treatment Exposure = the number of days of drug taken = drug stop date – start date + 1
- Treatment Compliance % = $[(\text{drug stop date} - \text{start date}) + 1 - \text{number of days drug not taken}] / [(\text{drug stop date} - \text{start date}) + 1] \times 100\%$.

A subject data listing will be provided for study drug dispense and return.

5.2 PRIOR AND CONCOMITANT THERAPY

Prior medications are defined as medications that started prior to the first dose of study drug in study 1042-0604. Concomitant medications are defined as medications (other than the study drug) taken on or after the first doses of the study drug during the study. Medications started before the first dose of study drug and continuing at the time of the first dose of study drug are considered both prior medication and concomitant medication. Medications with complete missing start/end date are considered both prior and concomitant medications.

All investigator terms for medications recorded on the CRF will be coded using the World Health Organization (WHO) Anatomical Therapeutic Chemical (ATC) drug dictionary (Version WHO Drug Dictionary, March 2014). The number (percentage) of subjects who took prior and concomitant medications will be summarized by treatment, i.e. Ganaxolone, in safety population, by ATC Classification and WHO Drug PT.

A subject data listing of prior and concomitant therapy will be provided.

To define prior or concomitant medication, the following table describes how missing date information will be handled

Partial Missing Start or Stop Date	Imputed Start Date	Imputed Stop Date
Missing month and day, and the year is present	January 1 of that year or first dose date if the year is the same as the year of first dose date	December 31 of that year
Missing day, but year and month are present	First day of that month or first dose date if the year and month are the same as the year and month of first dose date	Last day of that month
Missing month, but year and day are present	Missing month imputed as January	Missing month imputed as December

6. EFFICACY ANALYSES

All efficacy analyses will be performed for partial-onset seizure (POS) with or without secondary generalization only. POS seizures includes three seizure subtypes which are SPS-motor, CPS and SGTC.

All efficacy data will be summarized by treatment, i.e. Ganaxolone, in FAP.

6.1 MAIN EFFICACY ANALYSIS

The primary efficacy endpoint is the percentage change in POS seizure frequency per 28-days relative to baseline in study 1042-0603. Post-baseline 28-day seizure frequency will be calculated as the total number of seizures in this open-label extension study (Study 1042-0604) divided by the number of days with available seizure data in the post-baseline period, multiplied by 28. Baseline 28-day seizure frequency will be calculated as the total number of seizures in the baseline period of Study 1042-0603 (≤ 56 days) divided by the number of days with available seizure data in the baseline period, multiplied by 28. The calculation for percent change from baseline in 28-day seizure frequency will be done as follows for each subject:

$$\left(\frac{[(\text{Post-baseline 28-day seizure frequency}) - (\text{Baseline 28-day seizure frequency})]}{(\text{Baseline 28-day seizure frequency})} \right) \times 100\%$$

The baseline, post-baseline, and percent change from baseline in 28-day seizure frequency will be summarized by treatment, i.e. Ganaxolone, in FAP.

A subject data listing will be provided.

6.2 OTHER EFFICACY ANALYSIS

6.2.1 Responder rate, Proportion of subjects with $\geq 50\%$ reduction in 28-day seizure frequency compared with baseline.

A 50% responder is an individual whose reduction of percent change from baseline to the end of the open label extension period in 28-day POS seizure frequency is greater than or equal to 50%. The number and percentage of responders will be summarized.

A subject data listing will be provided.

6.3 SUBGROUP ANALYSIS

No subgroup analysis planned.

7. SAFETY ANALYSIS

All safety analyses will be performed by treatment, i.e. Ganaxolone, in the Safety Population. Safety assessments include:

- AE
- Clinical laboratory tests
- Vital signs including temperature, blood pressure, pulse rate, and weight
- 12-lead ECG
- Physical and neurological examinations
- Columbia-Suicide Severity Rating Scale (C-SSRS)

Baseline is defined as the last non-missing value obtained before the first treatment in the preceding Study 1042-0603.

7.1 ADVERSE EVENTS

Adverse events (AEs) will be coded by System Organ Class (SOC) and Preferred Term (PT) using the Medical Dictionary for Regulatory Activities (MedDRA®, version 16.0/AECODE). The verbatim term will be included in the AE listings.

A treatment-emergent adverse event (TEAE) is defined as an AE that occur or worsen on or after the first dose of study drug in Study 1042-0604 and before the end of the study (including the safety follow-up period). Only TEAEs will be included in summary tables. All AEs, treatment emergent or otherwise, will be presented in subject data listings.

The TEAEs will be summarized as the number (percentage) of subjects with TEAEs within SOC and PT. Subjects who report the same PT on multiple occasions will be counted once for the PT: under the highest severity (severe > moderate > mild) when summarized by severity and under the closest relationship (related > probably related > possibly related > unlikely related > Not related) to study drug when summarized by relationship. If a subject reports multiple PT for a SOC, the subject will be counted only once for that SOC. Treatment related AEs are defined as those events recorded on the CRF as 'Related', 'Probably Related' or 'Possibly Related', others will not be related AEs.

TEAEs will be summarized as below.

- An overview table, including number of subjects with
 - TEAEs
 - serious AEs (SAEs)
 - study drug related TEAEs
 - TEAEs by severity

- TEAEs leading to study discontinuation
- TEAEs leading to death
- TEAE by SOC and PT
- TEAE by SOC, PT, and Severity
- TEAE by PT
- TEAEs by SOC, PT, and Relationship to Study Drug

All AE tables will be sorted by SOC and PT in decreasing frequency of the number and percentage of subjects.

Missing date will be imputed followed table describes how missing date information will be handled:

Partial Missing Start or Stop Date	Imputed Start Date	Imputed Stop Date
Missing month and day, and the year is present	January 1 of that year or first dose date if the year is the same as the year of first dose date	December 31 of that year
Missing day, but year and month are present	First day of that month or first dose date if the year and month are the same as the year and month of first dose date	Last day of that month
Missing month, but year and day are present	Missing month imputed as January	Missing month imputed as December

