8.3.4.3 Consequences of Early Termination

The protocol specifies dose de-escalation of study medication over one to two weeks depending upon dose and duration of treatment. This recommendation is based on cumulative evidence from various classes of CNS drugs that slow taper is beneficial. It is possible that abrupt cessation of the drug might cause discontinuation symptoms. Every effort will be made to ensure implementation of the dose de-escalation.

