8.4.4 Selection of Doses in the Study

In meeting efficacy and tolerability criteria to participate in the study, it is expected that the subject will continue with the dose of ganaxolone (between 900-1800 mg/d) last prescribed in Study 1042-0603. Changes at V1 can be addressed with the Sponsor's Medical Monitor. During the study, the dose of ganaxolone may be adjusted at the Investigator's discretion based on tolerability and efficacy between 900 and 1800 mg/d, typically on the MTD of ganaxolone that provides adequate seizure control. Doses may be adjusted upward or downward in 225 mg/d increments every 3 days to reach an optimal dose level over the duration of the 52-week treatment period. Dose adjustments should be made with the investigator's agreement. Frequency of dosing changes may not be less than 3 days unless required for safety.

De-escalation Period: The study drug will be decreased in increments of 450mg/d in 4-day intervals over 12 days for 1800 mg. Decreases from doses less than 1800 mg will be adjusted accordingly (See [Table 2](#)). The subject will return for final post-taper safety assessment visit.

Details of the de-escalation regimen are provided in the table below.

Table 2. Dosing Schedule for De-Escalation Period

De-Escalation, Study Completion or Early Termination (ET)			
Visit	Taper Day	Dose (mg)/day	225 mg cap/day
Visit 7 (Study Completion/Early Term)	Last full dose	1800	8
	1	1350	6
	2	1350	6
	3	1350	6
	4	1350	6
	5	900	4
	6	900	4
	7	900	4
	8	900	4
	9	450	2
	10	450	2
	11	450	2
	12	450	2
	13	0	0
	14	0	0

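### The adverse event tables pool onset during maintenance, taper and post-taper follow-up, so they cannot show whether events cluster when ganaxolone is stopped

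*SAP*

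**What the plan says.** SAP 7.1 sets a single treatment-emergent window: an event qualifies if it occurs or worsens "on or after the first dose of study drug in Study 1042-0604 and before the end of the study (including the safety follow-up period"). It adds "Only TEAEs will be included in summary tables" and "All AEs, treatment emergent or otherwise, will be presented in subject data listings". On counting, "Subjects who report the same PT on multiple occasions will be counted once for the PT". The planned tables are an overview, SOC by PT, SOC by PT by severity, PT alone, and SOC by PT by relationship. SAP 7.1.1 adds listings of serious events, events leading to discontinuation, and deaths. None of these is divided by study phase.

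The protocol treats stopping as a phase of its own. Under 8.4.4 the drug is "decreased in increments of 450mg/d in 4-day intervals over 12 days for 1800 mg", and 8.3.4.2 asks for a taper of one to two weeks, where possible, after early termination. Visit 8 (8.5.1.3.8) is described as "follow-up for end of dose de-escalation period". Section 8.3.4.3 bases the taper on "cumulative evidence from various classes of CNS drugs that slow taper is beneficial" and says "It is possible that abrupt cessation of the drug might cause discontinuation symptoms".

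Protocol 8.7.1.4 also planned adverse event incidence by dose. SAP 7.1 has no such table, and SAP Section 9 does not list its removal as a change.

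**The concern.** Safety and tolerability are the primary objective. Two questions sit inside it: what happens while subjects take the drug, and what happens when they come off it. With one pooled count, an excess on stopping would appear only as a slightly higher total for the affected terms, with nothing to show when it arose.

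The counting rule adds to this. A subject who reports a term on maintenance and again during the taper contributes one count, so the recurrence is absent from every table.

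The relationship table does not fill the gap. The causality categories in Protocol 9.5.2 from possibly related upwards refer to temporal sequence from administration, and the two highest refer to response when the drug is withdrawn or reduced. None describes an event brought on by stopping. The by-dose tabulation might have set part of the taper apart, but it was dropped.

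**Working it through.** The plan gives no figure for this point, so the check covers the taper schedule, the share of the window after maintenance, and an illustration.

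**1. Taper schedule.** Inputs from Protocol 8.4.4: start 1800 mg/d, steps of 450 mg/d, 4 days per step.
- Dosed steps: 1350, 900 and 450 mg/d, so 3 × 4 = 12 days. This matches the stated 12 days and Table 2.
- Visit 8 is nominally 2 weeks after Visit 7, so 14 − 12 = 2 days are drug-free. If Visit 8 falls at the late end of its ±2-week window, 28 − 12 = 16 days are drug-free.
- Days 1–8 of this taper are at 1350 or 900 mg/d, inside the study's 900–1800 mg/d range.

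**2. Share of the window after maintenance.** Inputs: 104 weeks plus 2 weeks (Protocol synopsis). Formula: 14 / (7 × weeks on maintenance + 14).

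| Exit from maintenance | Calculation | Share |
|---|---|---|
| Week 104 | 14/742 | 1.9% |
| Week 52 | 14/378 | 3.7% |
| Week 17 | 14/133 | 10.5% |

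This assumes a full 14-day phase. Protocol 8.3.4.2 allows one week after early termination. If the phase were only 7 days, the share would be 7/371 = 1.9% at week 52 and 7/126 = 5.6% at week 17.

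**3. What pooling could do, under assumed rates.** The documents give no event rates for this phase. Assume a constant daily hazard λ on maintenance, k times higher during the 14 days. Incidence on maintenance is 1 − exp(−λd) for d maintenance days; pooled incidence is 1 − exp(−λ(d + 14k)).
- For a term with 10% incidence over 728 days, λ = −ln(0.90)/728. Take k = 10.
- Completer: 10.0% on maintenance, 11.8% pooled.
- Exit at week 17 (d = 119): 1.7% on maintenance, 3.7% pooled.
- With base incidence from 5% to 15% and k from 1 to 20, the pooled figure for completers is 0.1 to 5.2 percentage points above maintenance alone.

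These numbers show a mechanism and a range. They are not an estimate for ganaxolone. In every case the pooled table gives one figure, and a reader cannot tell which k produced it.

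**4. Partial dates.** Under SAP 7.1, a missing start day becomes the first of the month unless that month contains the first dose. If a taper begins mid-month and an event starts later that month with the day missing, imputation places the onset before the taper. This is harmless under the pooled definition but would misclassify events once periods are separated.

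**The case against.** The best case for the plan is that carrying follow-up into a treatment-emergent window is not an error, and the SAP states openly that it does so. Most of the phase is still on drug: 12 of 14 nominal days for a taper from 1800 mg/d. All events are listed by subject, and Protocol 9.5.2 requires start and end dates. Laboratory values, vital signs and C-SSRS are summarised by visit, and all three are scheduled at Visit 8. SAP Section 9 says that the study ended early with few subjects, and SAP 2.1 drops summary tables where data are sparse. With few subjects, someone can read the listings.

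All of this stands, and it rules out three stronger readings that a reader might infer:
- **That the protocol expects withdrawal symptoms.** It calls them possible, ties them to abrupt cessation, and presents the taper as a precaution drawn from other CNS drugs. The documents report no withdrawal signal.
- **That no withdrawal signal could be detected at all.** The dated listings and the Visit 8 summaries allow a case-level look.
- **That the treatment-emergent definition is wrong or mislabels events as on-treatment.** It does neither.

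The gap in the tables remains. The listings support a look after the fact, but no rule fixes in advance which events count as arising on stopping. The Visit 8 summaries do not cover adverse event terms. Abrupt stopping is also foreseeable: the early-termination taper applies only where possible, and Protocol 8.3.4.1 leaves open whether drug is stopped at once or tapered.

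**Conclusion.** The point holds as a limit on what the adverse event summary tables can show. They cannot separate onset during maintenance from onset during the taper or after the last dose, and once-per-term counting conceals recurrence on stopping. It is a matter of reporting clarity: no figure in the documents is wrong, and no inference is invalidated.

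The phase at issue is 1.9% of the window for a completer and up to 10.5% for exit at week 17, assuming 14 days of taper and follow-up; a one-week phase would give less. Early termination of the study raises the weight of this phase for subjects whose maintenance was cut short, but the documents do not say when subjects left or how many there were. The size of any excess of events on stopping is unknown. Severity is minor, and the change is a cheap improvement.

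**What to change.** Keep the treatment-emergent definition and the total column in SAP 7.1, and add an onset-period flag:
- (a) from the first 1042-0604 dose to the last dose before de-escalation starts, or to the last dose if there is no taper;
- (b) during de-escalation;
- (c) after the last dose to the end of follow-up.

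Define the periods by the start of de-escalation and not by dose in mg, because 900 mg/d can be maintenance for one subject and a taper step for another.

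Then:
- Present the overview and the SOC by PT table for (a), for (b) and (c) combined, and in total. If data are sparse under SAP 2.1, show the flag as a column in the adverse event listing instead.
- Count each subject once per PT within each period, with subjects who entered that period as its denominator.
- State in SAP 5.1 whether the drug stop date includes the taper.
- Flag events whose partial onset date could fall in more than one period, and do not let first-of-month imputation assign them to maintenance.
- Restore the by-dose tabulation of Protocol 8.7.1.4 or list its removal in SAP Section 9.

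The cost is SAP wording and a few columns. Adverse event dates, the Visit 7/ET date and drug stop dates are already part of the planned data, once the meaning of the stop date is settled. The downside is slightly longer tables with small counts.
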